## 4. INVESTIGATIONAL PLAN

### 4.1. Overall Study Design and Plan

This is a Phase 2, single arm, multicenter, international study to assess the safety and efficacy of single agent CC-486 (oral azacitidine) in previously treated subjects with locally advanced or metastatic NPC, who have progressed (clinically or radiographically) after having received 1 or 2 previous regimens, including a platinum-based chemotherapy. The primary endpoints are overall response rate (ORR) and progression-free survival (PFS).

Approximately 51 to 55 efficacy evaluable subjects will be enrolled according to Simon's optimal two-stage design; if the predefined activity is met (> 4 responses [complete response (CR)/partial response (PR)] out of the first 17 efficacy evaluable subjects based on independent radiological assessment), then the study will continue to enroll an additional 34 efficacy evaluable subjects. If  $\leq$  4 responses out of 17 are observed, then the study enrollment will be stopped. The Stage 1 decision will be based on ORR only, and the Stage 2 decision will be based on both ORR and PFS. Subjects who are not evaluable for efficacy will be replaced at the discretion of the sponsor. Subjects who are discontinued from study prior to the first tumor assessment for any reason other than for progressive disease are not evaluable and will be replaced. Subjects who progress prior to the end of Cycle 1 are not evaluable and will be replaced.

The study will consist of the following visits:

**Screening Assessments:** Screening evaluations will be performed for all subjects to determine study eligibility. These evaluations must be completed within 21 days of first dosing unless otherwise noted.

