**Treatment:** Subjects meeting eligibility criteria must start treatment within 21 days of signing the informed consent form (ICF). For all subsequent visits, an administrative window of  $\pm$  2 days is permitted. Treatment cycles are 21 days in duration. All evaluations should be performed prior to dosing on the visit day, unless otherwise specified. CC-486 will be administered at a dose of 300 mg orally (PO) daily (QD) on Days 1 to 14 of a 21-day cycle. However, the first 6 subjects of Asian-Pacific Island ethnicity evaluable for safety will receive CC-486 at a dose of 200 mg orally QD on Days 1 to 14 of 21 days of Cycle 1; and if well-tolerated, and there are no safety concerns, subsequent subjects of Asian-Pacific Island ethnicity will be treated at the 300 mg QD on Days 1 to 14 of a 21-day cycle.

**Response Assessment by Response Evaluation Criteria In Solid Tumors (RECIST) v 1.1:** Response assessments (tumor evaluations) should be performed at screening within 28 days before the start of investigational product (IP), and every 6 weeks ( $\pm$  5 days) from Cycle 1 Day 1 (C1D1) for the first 3 tumor evaluations and then every 9 weeks until disease progression, start of a new anticancer therapy, or withdrawal of consent from the entire study. Evaluation of response will be performed using RECIST v1.1.

An independent radiological assessment of responses will be conducted using RECIST v1.1.

Response assessments include computed tomography (CT) scan or magnetic resonance imaging (MRI) of the head and neck with supraclavicular node imaging, the chest and abdomen/pelvis,

neurological examination with facial nerve evaluation, and bone scans at baseline for all subjects. Bone scans will be repeated only if the subject is symptomatic or with known bone metastasis. The same mode of imaging for lesion evaluation at screening must be used consistently throughout the study.

All subjects with evidence of objective tumor response (CR or PR) should have the response confirmed with repeat assessments at the next scheduled scan, but after no less than 4 weeks. Response assessments must have occurred  $\geq$  6 weeks from Cycle 1 Day 1 to be considered as SD for a best response.

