## 10. EFFICACY ANALYSIS

All efficacy results will be summarized for the efficacy evaluable population. If Stage 2 is conducted, analyses will be performed for PFS and OS in addition to ORR. Column headers will be displayed as follows: 'AP 200 mg', '300 mg', and 'Total'.

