### 10.2. Analysis of the Efficacy Endpoints

The primary efficacy endpoints are ORR and PFS.

Overall response rate is defined as the combined incidence of CR and PR, confirmed no less than 4 weeks after the criteria for response are first met, based on independent radiology assessment using RECIST version 1.1. After the enrollment of 51 patients, if more than 14 responders are observed, the null hypothesis ( $ORR \leq 20\%$ ) will be rejected, the true ORR will be concluded to be  $> 20\%$ . The point estimate and two-sided 90% CI of ORR will be provided using the Clopper-Pearson method (Clopper, 1934).

Progression-free survival will be based on independent radiology assessed response using RECIST v1.1. Progression-free survival is defined as the time from the date of start of the study treatment to the date of disease progression or death (any cause) on or prior to the data cut-off date for the statistical analysis, whichever occurs earlier. Subjects who do not have disease progression or have not died as of the data cut-off date will be censored at the time of the last radiologic assessment prior to the data cut-off date. In the event that a new anticancer therapy is initiated for a subject prior to documented progression, the subject will be censored at the time of the last radiologic assessment where the subject was documented to be progression-free prior to the initiation of the new anticancer therapy. Subjects with a single missing radiologic assessment prior to a visit with documented disease progression (or death) will be analyzed as a PFS event at the time of the radiologic assessment that shows progression (or death). Subjects with  $\geq 2$  consecutive missing radiologic assessments prior to a visit with documented disease progression (or death) will be censored at the time of the last radiologic assessment where the subject was documented to be progression-free prior to the first of the  $\geq 2$  consecutive missing visits.

The Kaplan-Meier (K-M) method will be used to estimate PFS distribution, and the medians with two-sided 90% CIs will be reported. Since the study did not enter the second stage, no hypothesis testing will be conducted for PFS. The K-M estimates of PFS rates at each 2-month interval will be provided. Kaplan-Meier curves for PFS will be presented.

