## 18. APPENDICES

### 18.1. Study schematic

### 18.2. Handling of Dates

Dates will be stored as numeric variables in the SAS analysis files and reported in DDMMYY format (eg, the Date9. datetime format in SAS). Dates in the clinical database are classified into the categories of procedure dates, log dates, milestone dates, outcome dates, and special dates.

- **Procedure Dates** are the dates on which given protocol-specified procedure are performed. They include the dates of laboratory testing, physical examinations, tumor scans, etc. They should be present whenever data for a protocol-specified procedure are present and should only be missing when a procedure are marked as NOT DONE (ND) in the database. Procedure dates will not be imputed.
- **Log Dates** are dates recorded in the CRF data logs. Specifically, they are the start and end dates for AEs and concomitant medications/procedures. They should not be missing unless an event or medication is marked as *ongoing* in the database. Otherwise, incomplete log dates will be imputed according to the rules in Appendix

17.2 (eg, for duration or cycle assignment). However, in listings log dates will be shown as recorded without imputation.

- **Milestone Dates** are dates of protocol milestones such as randomization, study drug start date, study drug termination date, study closure date, etc. They should not be missing if the milestone occurs for a subject. They will not be imputed.
- **Outcome Dates** are dates corresponding to study endpoints such as survival and disease progression. In most cases they are derived either from a milestone (e.g., the survival date is derived from the death date), or a procedure date (e.g., the disease progression date is derived from the date of the tumor scan that was used to determine disease progression). They may be subject to endpoint-specific censoring rules if the outcome did not occur, but are not otherwise subject to imputation.
- **Special Dates** cannot be classified in any of the above categories and they include the date of birth. They may be subject to variable-specific censoring and imputation rules.

Dates recorded in comment fields will not be imputed or reported in any specific format.

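### Do the 2-month Kaplan-Meier PFS rates misstate PFS because months 4 to 12 each fall shortly before a scan?

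*SAP*

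**What the plan says.** Section 10.2 of the SAP defines PFS from the start of study treatment to independently assessed progression or death. It plans a Kaplan-Meier median with a 90% confidence interval, Kaplan-Meier curves, and landmark rates: "The K-M estimates of PFS rates at each 2-month interval will be provided".

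Section 4.1 sets the scan calendar: "every 6 weeks ( $\pm$ 5 days) from Cycle 1 Day 1 (C1D1) for the first 3 tumor evaluations", with 9-week spacing after that. Section 18.2 fixes the event date: "the disease progression date is derived from the date of the tumor scan that was used to determine disease progression".

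Two statements settle what PFS is used for. Section 4.1: "The Stage 1 decision will be based on ORR only, and the Stage 2 decision will be based on both ORR and PFS". Section 10.2: "Since the study did not enter the second stage, no hypothesis testing will be conducted for PFS".

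The opening of Section 10 adds: "If Stage 2 is conducted, analyses will be performed for PFS and OS in addition to ORR".

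**The concern.** The scan calendar and the 2-month reporting grid share the same origin but do not line up. From month 4 on, every landmark comes late in a scan interval, just before the next scan. Progressions that arise in that interval and are found at the next scan do not yet count. The rate labelled 6 months is therefore close to the rate after the week-18 scan, and the one labelled 8 months is close to the rate after week 27. The shift always favours the drug, so it does not average out across landmarks.

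PFS is one of two primary endpoints, and Section 4.3 names a 50% PFS rate at 5 months as a benchmark. A reader who takes the 6-month figure as the proportion truly free of progression at 6 months would be too optimistic.

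A second point of wording seems to add to this. The opening of Section 10 ties PFS analysis to Stage 2, while Section 10.2 says Stage 2 was not entered and still reports PFS.

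**Working it through.** The SAP gives no figure for these rates, so there is none to reproduce.

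**Inputs from the SAP.** Scans at weeks 6, 12, 18, 27, 36, 45 and 54 are days 42, 84, 126, 189, 252, 315 and 378 (Section 4.1). Progression is dated at the scan (Section 18.2). The median of 5 months is the null value in Section 4.3. Stage 1 has 17 subjects (Section 4.3).

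**Assumptions.** A month of 30.4375 days (the SAP states no length), exponential time to progression or death, and 20% of events being deaths with exact dates.

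**Step 1: calendar.**

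| Month | Day | Days since last scan | Days to next scan |
|---|---|---|---|
| 4 | 121.8 | 37.8 | 4.2 |
| 6 | 182.6 | 56.6 | 6.4 |
| 8 | 243.5 | 54.5 | 8.5 |
| 10 | 304.4 | 52.4 | 10.6 |
| 12 | 365.2 | 50.2 | 12.8 |

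The described pattern is there. A 30-day month gives 6 to 18 days to the next scan; a 28-day month gives 14 to 42.

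**Step 2: size of the gap.** The underlying rate is S(t) = exp(−ln 2 · t/5), with t in months. If scans are exactly on schedule, the scan-dated rate at a landmark is S(last scan) − 0.20 × [S(last scan) − S(landmark)]. At month 6 the last scan is day 126, which is 126/30.4375 = 4.14 months:

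- S(4.14) = 56.3%; S(6) = 43.5%.
- Scan-dated rate: 56.3 − 0.20 × (56.3 − 43.5) = 53.8%.
- Gap: about 10 points.

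Simulation with scans spread uniformly over ±5 days gives these rates:

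| Month | Scan-dated rate | Underlying rate | Gap (points) |
|---|---|---|---|
| 4 | 65.5% | 57.4% | 8.0 |
| 6 | 53.8% | 43.5% | 10.3 |
| 8 | 40.4% | 33.0% | 7.4 |
| 10 | 30.3% | 25.0% | 5.3 |
| 12 | 22.8% | 18.9% | 3.8 |

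At month 6 the gap runs from 12.8 points with no exactly dated deaths to 7.7 with 40%, and from 10.8 to 8.3 for medians of 3 to 8 months.

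**Step 3: what the gap is measured against.** The underlying rate refers to the moment the tumour would have met the progression criteria had it been watched continuously. The trial does not observe that moment, and the SAP does not define PFS by it. Taken together, Sections 10.2 and 18.2 make the endpoint the time to the scan showing progression, or to death. The Kaplan-Meier value at month 6 estimates the probability that this defined time exceeds 6 months. In the example that probability is 53.8%, and that is what the table would show. The 10 points separate two different quantities; they are not a bias in estimating the stated one.

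**Step 4: what scan-aligned rates would add.** Read at day 132, after the week-18 window closes, the scan-dated rate is 56.1% against an underlying 54.8%, a gap of 1.3 points. Compared with the planned month-6 figure, the percentage moves by 56.1 − 53.8 = 2.3 points. The extra row carries almost the same percentage under an earlier time.

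**Step 5: scale.** With 17 subjects analysed, one subject is 1/17 = 5.9 points. The 90% half-width at month 6, by the normal approximation without censoring, is 1.645 × √(0.538 × 0.462/17) = 0.199, about 20 points. The month-6 gap is under two subjects (10.3/5.9 = 1.7).

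**Step 6: Section 10 against Section 10.2.** Section 10 says what is analysed if Stage 2 takes place. It does not rule out PFS analysis otherwise. Section 10.2 is written knowing that Stage 2 was not entered: it drops the PFS test for that reason and keeps the median, the rates and the curve. The specific text tells the analyst exactly what to produce.

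**The case for a change.** The strongest case for the concern is that a wide interval describes random error and does nothing about a systematic label. All five landmarks from month 4 to month 12 err in the same direction, and a table headed by round months does not tell the reader so. With a true median of 5 months, the 6-month entry of about 54% could be read against the 50% benchmark as encouraging. The remedy would cost a few rows and a footnote.

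The arithmetic stands, and so does the observation that scan-dated rates should be read with the schedule in mind. The sample-size argument alone would not dismiss it. What fails is the step from there to a fault in the plan. The schedule is stated in the SAP, the dating rule is stated, and the planned curve displays the plateaus and drops. The 5-month benchmark is not one of the 2-month time points, and no test against it will be run. An interval-censored estimate would target a different quantity from the defined endpoint and would be imprecise with about 17 subjects.

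The absolute percentages above also come from an unselected cohort, whereas the table uses the Efficacy Evaluable Population of Section 5.2.3. Removing deaths before day 84 and progressions before day 21 as a rough stand-in moves the month-6 figures to 62.2% against 50.3%. The gap, 62.2 − 50.3 = 11.9 points, stays similar, so this affects the illustration and not the argument.

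On Sections 10 and 10.2, the conditional sentence is untidy. It could have been updated when Section 10.2 was, but doing so would change no output.

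**Conclusion.** The concern does not hold. The calendar mismatch is real, and under the stated assumptions it puts the 2-month rates about 4 to 10 points above an underlying progression-free proportion. That proportion is not the endpoint. The SAP dates progression at the scan, Kaplan-Meier is valid for that endpoint, and Sections 4.1, 10.2 and 18.2 agree with each other. The rates are descriptive, the Stage 1 decision uses response only, and scan-aligned rows would mostly relabel percentages already in the table. The wording of Section 10 on Stage 2 does not conflict with what Section 10.2 instructs.

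The sizes rest on an assumed month length, exponential event times, a ±5-day window on all scans (not restated for the 9-week ones), the share of exactly dated deaths, and 17 analysed subjects. The conclusion does not depend on them: it follows from how the SAP defines PFS and from the absence of any decision based on these rates.

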### **10.3. Analyses of Other Evidence of Anti-cancer Activities**

The number and percentage of subjects who received any anticancer therapy post-treatment will be summarized overall and by therapy categories. The time from study treatment discontinuation to the earliest date of anticancer therapy initiation will be summarized descriptively. Listings will be provided for each posttreatment anticancer therapy category.

### **10.4. Eastern Cooperative Oncology Group Performance Status**

A by-subject ECOG listing will be provided.

## 11. SAFETY ANALYSIS

All safety analyses will be conducted based on the safety population. Descriptive statistics will be provided by treatment dose and for total safety population.

### 11.1. Adverse Events

Adverse events will be analyzed in terms of TEAEs which are defined as any AE that begins or worsens on or after the start of study drug through 28 days after the last dose of study drug. All AEs will be coded using MedDRA version 19 or higher.

A treatment-related TEAE is defined as a TEAE which was reported as “Suspected” on the CRF. Adverse events with a missing relationship will be treated as “treatment-related.”

The incidence of TEAE will be summarized by MedDRA SOC and PT. Severity of AEs will be graded 1 to 5 according to the CTCAE Version 4.0 or higher. For all other AEs not described in the CTCAE, severity will be assessed by the investigator as mild (Grade 1), moderate (Grade 2), severe (Grade 3), life-threatening (Grade 4) or death (Grade 5).

Tables summarizing the number and percentage of subjects experiencing TEAEs by treatment dose and for total safety population will be generated for each of the following:

- All TEAEs by SOC and PT
- All TEAEs by SOC
- All TEAEs by PT
- All TEAEs by Preferred term with Incidence of >5%
- All TEAEs by onset cycle
- Treatment-related TEAEs
- TEAEs of Grade 3 or 4
- Treatment-related TEAEs Grade 3 or 4
- All TEAEs by maximum CTCAE grade
- Treatment-related TEAEs by maximum CTCAE grade
- Serious TEAEs
- All serious TEAEs by Preferred term with Incidence of >5% Treatment-related serious TEAEs
- All treatment-related serious TEAEs by Preferred term with Incidence of >5%
- TEAEs with action of study drug withdrawn
- Treatment-related TEAEs with action of study drug withdrawn
- TEAEs with action of study drug dose reduced

- Treatment-related TEAEs with action of study drug dose reduced
- TEAEs with action of study drug dose interrupted
- Treatment-related TEAEs with action of study drug dose interrupted
- TEAEs with outcome of death
- Treatment-related TEAEs with outcome of death
- All deaths within 28 days of last dose with cause of death
- TEAEs for the following baseline subgroups (provided the number of subjects is sufficient):
  - Age (< 65 years, 65 years to < 75 years, ≥ 75 years)
  - Sex

For summaries by severity, if a subject experiences the same AE more than once with different toxicity grades, the event with the maximum grade will be tabulated in “by maximum grade” tables. If a subject experiences multiple occurrences of AEs under the same SOC and/or PT, the subject will be counted only once for that SOC and/or PT. In addition, AEs with a missing intensity will be presented in the summary table with an intensity category of “Missing.”

Listings will be prepared that include the verbatim term, PT, and SOC as well as full details of all AEs for subjects in the safety population.

Separate listings will also be prepared for serious TEAEs, TEAEs leading to death, and TEAEs resulting in discontinuation of IP. All deaths will be listed with the cause of death collected on the Death CRF page.

## 11.2. Adverse Events of Special Interest

### 11.2.1. AE of Special Interest

The selected AEs of special interest refers to a group of terms/PTs from one or more SOCs relating to a defined medical condition or area of interest. The following AEs of Special Interest are based on risk definitions (search criteria) as outlined in the Vidaza RMP currently approved at the time of data cut-off date:

- Myelosuppression (neutropenia, thrombocytopenia, anemia, general myelosuppression)
- Haemorrhagic events
- Infections
- Renal failure
- Hepatic failure
- Ischemic colitis
- Interstitial lung disease

- Tumor lysis syndrome
- Cardiac disorders (cardiac failure, cardiac arrhythmias and myocardial infarction)
- Anxiety, confusion, insomnia
- Other psychiatric disorders

After review of the data, there may be other AEs of special interest identified. The following summaries will be provided for TEAEs included in the above-mentioned AEs of special interest:

- All TEAEs
- TEAEs of Grade 3 or 4
- Serious TEAEs
- TEAEs leading to study drug withdrawal
- TEAEs leading to study drug dose reduction
- TEAEs leading to study drug dose interruption
- TEAEs leading to death

Additional safety analyses may be performed by specific parameters (eg, time to occurrence), if warranted.

### **11.2.2. Dose Limiting Toxicity**

Dose limiting toxicity (DLT) is defined in the protocol and will be evaluated only for the first 6 subjects of Asian-Pacific Island ethnicity evaluable for safety (receiving 200 mg QD of CC-486). A summary table of DLTs will be presented including number and percentage of subjects having DLT.

A flag for DLTs may be added to selected listings of AEs as appropriate.

## **11.3. Clinical Laboratory Evaluations**

Clinical laboratory values will be graded according to CTCAE version 4.0 for applicable tests. Normal ranges will be used to determine the categories high, low, and normal for laboratory tests. Listings will be provided for all clinical lab evaluations with normal ranges included.

### **11.3.1. Hematology, Chemistry, Urinalysis, and Coagulation**

The laboratory values will be graded using CTCAE v4.0 for applicable tests as follows:

- Hematology: red blood cell count, hemoglobin, hematocrit, white blood cell count, absolute neutrophil count, absolute lymphocytes, absolute monocytes, absolute eosinophils, absolute basophils, and platelets.
- Chemistry: sodium, potassium, calcium, magnesium, phosphorus, blood urea nitrogen, creatinine, uric acid, glucose, lactate dehydrogenase, total protein, albumin, alkaline phosphatase, bilirubin (total and direct), aspartate aminotransferase/serum glutamic oxaloacetic transaminase, alanine aminotransferase.

For laboratory values that fall outside the grade criteria of CTCAE v4.0 for laboratory tests listed above, a Grade of 0 will be assigned.

For hematology and chemistry, the number and percentage of subjects that have each CTCAE grade will be summarized using the most severe grade overall during the treatment for each of the applicable tests. A shift table representing the shift from the baseline grade to the most severe grade during treatment will be provided for all applicable laboratory tests listed above. For coagulation, a listing will be provided. The onset day of nadir across all cycles, the analyte value at nadir, and the change from baseline to analyte value at nadir will be summarized descriptively.

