## 11.4. Vital Sign Measurements

For vital signs, a shift table from baseline to worst post-baseline will be displayed for temperature, systolic and diastolic blood pressure and pulse by normal range categories (low/normal/high). Normal ranges given in [Table 2](#) will be used to determine the categories low, normal and high. A by-subject listing will be provided.

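### The nadir summary is not limited to hematology and no peak is summarised, and vital signs get one undefined 'worst' category on a two-sided scale

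*SAP*

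**What the plan says.** SAP section 11.3.1 covers hematology, chemistry, urinalysis and coagulation. The chemistry list runs from "Chemistry: sodium, potassium, calcium, magnesium, phosphorus, blood urea nitrogen, creatinine, uric acid, glucose" through to "bilirubin (total and direct), aspartate aminotransferase/serum glutamic oxaloacetic transaminase, alanine aminotransferase", with LDH, total protein, albumin and alkaline phosphatase in between. The section then plans these outputs:

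- **Worst grade.** For hematology and chemistry, CTCAE grades are "summarized using the most severe grade overall during the treatment for each of the applicable tests".
- **Grade shift.** "A shift table representing the shift from the baseline grade to the most severe grade during treatment will be provided for all applicable laboratory tests".
- **Coagulation.** A listing only.
- **Nadir.** In the next sentence, "The onset day of nadir across all cycles, the analyte value at nadir, and the change from baseline to analyte value at nadir" are to be summarised descriptively. No panel or test is named.

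Values outside the CTCAE criteria are assigned Grade 0. Section 11.3 adds "Normal ranges will be used to determine the categories high, low, and normal for laboratory tests", but no laboratory table in 11.3 or 11.3.1 uses those categories. It also promises listings of all laboratory values with normal ranges.

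For vital signs, section 11.4 says "a shift table from baseline to worst post-baseline will be displayed for temperature, systolic and diastolic blood pressure and pulse by normal range categories", on a low/normal/high scale. Table 2 gives two-sided ranges, for example 100 to 140 mmHg for systolic pressure. Which value counts as worst is not defined.

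**The concern.** Apart from the EBV-DNA summary in 11.3.2, the nadir is the only continuous laboratory summary in section 11.3. A nadir suits blood counts, where low is the harmful direction. For creatinine, bilirubin or the transaminases, the lowest value is the least adverse one the subject had. A programmer following the sentence as written would produce nadir rows for these tests and no row showing how far, or on which day, they rose.

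Direction is a problem in two further places. A single worst category for a vital sign cannot represent a subject who was low on one occasion and high on another, and two programmers could resolve that case differently. The laboratory grade tables take one most severe grade per test. Where a test can be abnormal both ways, such as sodium, potassium or glucose, the plan does not say that low and high are kept apart.

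Laboratory abnormalities are part of the safety secondary endpoint (section 4.1.2), and renal failure and hepatic failure are adverse events of special interest (section 11.2.1). The tables for their marker tests should be able to show a rise.

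**Working it through.** The SAP gives no figure to reproduce here. The check is what each planned table can show. All values below are invented for illustration.

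**1. A chemistry test with a rise.** Take creatinine at baseline 80, then 90, 160 and 75.
- Nadir: min(90, 160, 75) = 75; change 75 − 80 = −5.
- Maximum: max(90, 160, 75) = 160; change 160 − 80 = +80.
- The nadir summary reports a fall of 5. The worst-grade and shift tables use the 160 if it meets a grade criterion. The +80 and its day appear only in the listing.

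**2. A rise below Grade 1.** Under 11.3.1 it is Grade 0. The grade tables then show no change, the nadir is taken from another visit, and the unused high/low/normal categories of 11.3 do not fill the gap. No summary table shows the rise.

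**3. How the nadir reacts to a rise on average.** Assume a baseline and n post-baseline values per subject, all independent and normal with SD 1. The expected change to nadir is then minus the expected maximum of n standard normals, written e(n), plus any sustained shift d: d − e(n). Standard values are e(2) = 0.56, e(3) = 0.85, e(4) = 1.03, e(7) = 1.35 and e(8) = 1.42.

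| Case | Expected change to nadir (SD) |
|---|---|
| n = 8, no effect | 0 − 1.42 = −1.42 |
| n = 8, all values up by 1 SD | 1 − 1.42 = −0.42 |
| n = 8, one value up by 10 SD | minimum comes from the other 7: −1.35 |

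The expected change to the maximum is +1.42 SD with no effect and about +10 SD with the spike. The sustained-rise result depends on n. With d = 1 the change to nadir is +0.44 for n = 2, +0.15 for n = 3 and −0.03 for n = 4, so it appears as a fall from n = 4 upward. For a brief spike, going from n to n − 1 informative values moves the nadir little: 1.42 − 1.35 = 0.07 SD at n = 8.

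**4. A vital sign abnormal both ways.** Take systolic pressure at baseline 120, then 92 and 155. Against Table 2, 92 is below 100 (low) and 155 is above 140 (high). The shift table has one post-baseline category per subject. Either normal-to-low or normal-to-high is recorded, the other is lost, and the SAP does not say which.

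**5. A laboratory test graded both ways.** If low and high grades share one row, a low Grade 1 at baseline and a high Grade 3 on treatment give a 1-to-3 shift with no direction. A lesser on-treatment abnormality in the opposite direction drops out. Whether they share a row is not stated.

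**The case against.** The case on the other side has several parts.

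- **Scope.** The SAP does not say that chemistry is summarised at its nadir. The sentence names no panel and directly follows the coagulation listing, and a wholly unrestricted reading would reach coagulation too, which sits badly with a listing only. This stands: the chemistry reading is a literal one, not a stated intention. But if hematology alone was meant, the text does not say so, and chemistry then has no continuous summary at all. Either way the sentence needs correcting.
- **Rises are covered elsewhere.** A reader might infer that the plan reports renal and liver rises at their best value, or hides them. The documents do not support that. Graded rises enter the worst-grade and shift tables, section 5.1 brings in unscheduled assessments and refers to worst grades by cycle, all values are listed, and section 11.2.1 summarises renal and hepatic failure events in their own right. What is missing is narrower: the size and day of a rise, and rises below Grade 1.
- **Merged laboratory grades.** That low and high grades are combined is inferred from silence, and table shells may separate them. This stands, so the laboratory point is only that no split is stated. It also does not touch the renal and liver tests, where a rise is the concern.
- **Invented inputs.** The figures in the working are illustrative. They show how a minimum behaves and estimate nothing in this trial.
- **Low stakes.** This is descriptive output in a single-arm study that section 10.2 says did not enter its second stage. That bears on severity but does not make the rules sound.

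**Conclusion.** The point holds in limited form and is minor. As written, the only continuous summary in 11.3.1 is at the nadir, with no restriction to hematology and no maximum for any test. For chemistry tests whose harmful direction is up, that is the least informative value. The gap is confined to the size and day of a rise and to ungraded rises.

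The vital-sign part is the firmest, because it needs no reading between the lines: the scale is two-sided, the category is single, and the term is undefined. The laboratory grade tables share the weakness to the extent that low and high are not separated, which the SAP leaves unstated.

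No primary endpoint, hypothesis or stopping rule is affected. How many subjects would be affected cannot be estimated from the document. The conclusion assumes that the SAP text governs and that no table shell already settles these points.

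**What to change.** In section 11.3.1:
- Limit the nadir summary to named hematology tests and to analytes where low is adverse, such as albumin.
- Add value, day and change from baseline at the maximum for creatinine, blood urea nitrogen, uric acid, bilirubin, ALT, AST, alkaline phosphatase and LDH.
- Present the worst-grade and shift tables separately for low and high wherever a test is graded in both directions.

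In section 11.4, replace the single worst shift with two: baseline to lowest category and baseline to highest category.

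The cost is SAP wording, table shells and a few extra rows. All the values are already collected, so no new data are needed. The change is best made before database lock.
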